4.3. Safety Evaluation

Safety outcome measures are secondary endpoints and will be analysed as proportion of all implanted subjects using descriptive statistics. Safety information will be collected during the following intervals: during hospitalisation, interval from discharge to 4-weeks visit, interval after the 4-weeks visit including 8-weeks visit, interval after the 8-weeks visit including 16-weeks visit, interval after the 16-weeks visit including 24-weeks visit, interval after the 24-weeks visit including 36-weeks visit, and interval after the 36-weeks visit including 52-weeks visit.

Secondary endpoints are:

- Proportion of implanted subjects with treatment emergent adverse events. Treatment emergent adverse events are defined as events with onset during or after the implantation procedure.
- Proportion of implanted subjects with peristomal skin lesions will be evaluated using a validated 5-point scale by assessing signs of erythema, erosion, or papular lesions.
- Proportion of implanted subjects with device-related adverse event.
- Proportion of implanted subjects with device displacement, device revision or device replacement.

Photographs of the stoma are to be taken to document the ingrowth into the TIES® Port, surrounding peristomal skin and position of the implant at 4, 8, 16, 24, 36 and 52 weeks after implantation. At least 4 views are to be taken: horizontal, vertical frontal, vertical right and vertical left. Additional views may be required if skin lesions or device displacement develop.

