	
A Data Safety Monitoring Board will be appointed to review interim study results as discussed in section 9. A dermatologist will provide independent review of photographs of the stoma for peristomal skin lesions as required.

CLINICAL INVESTIGATION PLAN

Schedule of Assessments / Flow Chart:

Parameter/ Examination	Screening	Baseline ^a	Procedure (day 0)	Post OP (Daily follow up ^c)	Discharge	Visit 1 at 4 Weeks (+/- 7d)	Visit 2 at 8 weeks ^e (+/- 7d)	Visit 3 at 16 weeks (+/- 7d)	Visit 4 at 24 weeks (+/- 14 d)	Visit 5 at 36 weeks (+/- 14 d)	Visit 6 at 52 weeks (+/- 14 d)
Informed Consent		X									
Medical history	X	X									
Inclusion/Exclusion criteria	X	X									
Physical Examination ^f	X	X		X	X	X	X	X	X	X	X
Dipstick urine-analysis		X									
ECG		X									
Pregnancy test ^b		X									
Hematology and Chemistry		X									
Review and instruct on care of the stoma				X	X	X	X	X	X	X	X
Removal of Turnbull Adaptor ^d						X					
Start to use TIES® Lid							X				
Adverse Events (AE)			X	X	X	X	X	X	X	X	X
Safety evaluation			X	X	X	X	X	X	X	X	X
Concomitant medications		X	X	X	X	X	X	X	X	X	X
Ingrowth assessment						X	X	X	X	X	X
Photographs ^g of implant, stoma and adjacent skin			X		X	X	X	X	X	X	X
QOL questionnaires		X					X	X	X	X	X
Performance Questionnaire (Diary covering one 72-hours period)								X	X	X	X
Subject's preference questionnaire											X

^a The patient will be considered as enrolled only when the consent will have been signed. All the examinations performed before the enrolment are done according to routine practice at the hospital where the study takes place.

The baseline assessment should be performed not earlier than 12 weeks before the procedure.

^b Pregnancy test will be performed in woman of childbearing potential.

^c A follow up will be performed every day after the procedure prior to discharge from hospital.

^d Removal of Turnbull system will be performed at 4 weeks (+/- 7 days) only if it has not already detached by itself.

^eThe patient will continue to permanently use stoma bags until visit at 8 weeks for review of suitability to start using the TIES®Lid. If trimming of ileum is required, postpone use of TIES® Lid by about a week for healing.

^f Physical examination also includes weight measurement

^g At least 4 views of the stoma should be taken: horizontal, vertical frontal, vertical right and vertical left. Additional views may be required if skin lesions or device displacement develop.

CLINICAL INVESTIGATION PLAN

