6.5. Baseline Visit

The baseline visit may be combined with the screening visit. A full medical history including concomitant medications and physical examination will be performed in accordance with standard of care. Subjects will be assessed according to the eligibility criteria. They will not undergo any tests or procedures that are study specific and are not standard clinical practice until informed consent has been provided.

Each subject will be given a Subject Identification Number for tracking purposes and it is intended to assure confidentiality for subjects.

After confirming that all the inclusion and exclusion criteria are met, Informed consent will be discussed.

The following examinations are regarded as part of pre-operative assessment and the results are to be recorded in the medical case notes in accordance with requirements of the institution where the surgical procedure will be performed:

- Demographics, medical history and concomitant medications
- Physical examination
- Pregnancy test in woman of childbearing potential
- Pre-operative ECG
- Hematology and Chemistry
- Dipstick urine analysis
- Assessment by the stoma/research nurse and siting of stoma if required

The following information will be collected in the case report forms (CRFs):

- Demographics
- Medical history including indications for ileostomy and previous surgeries
- Concomitant medications
- Document in CRFs if the following procedures have been performed and any abnormal findings: physical examination, pre-operative ECG, hematology and chemistry tests, dipstick urine analysis
- Record if pregnancy test has been performed and the result
- Record if assessment by the stoma/research nurse has been performed and any abnormal findings
- Quality of Life (QoL) Questionnaire/s

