8.4. Investigator Reporting Responsibilities

The investigator should report to the sponsor the following events, whether expected or not, in the corresponding CRF form, with the exception of AEs / SAEs detected before the patients has signed the patient consent form.

- AE
- SAE
- Device Deficiencies that did not but might have led to a SAE if:
 - o Suitable action has not been taken or
 - o Intervention had not been made or
 - o If circumstances had been less fortunate
- New findings/updated in relation to already reported events

If an AE / SAE is present at the beginning of study prior to the subject providing signed consent to participate in the study, only its worsening should be reported.

The investigator will document all AEs on the Adverse Event Form, including (at a minimum) a description of the event, date of onset, severity, relationship to the investigational device and/or procedure, required interventions, duration, and outcome. The investigator will monitor all AEs until they are resolved, determined to be a chronic condition or the subject is lost to follow-up. The investigator will report all AEs regardless of whether it is anticipated or unanticipated and regardless of classification, seriousness, intensity, outcome or causality.

All Serious Adverse Events including all device deficiencies that could have led to a SAE should be reported to the Sponsor within 24 hours of awareness of an event via the Adverse Event electronic Case Report Form in the study's electronic database, as that will trigger an immediate e-notification to the Sponsor and Devicia. All device deficiencies should also be reported without unjustified delay.

If the e-CRF is unavailable, notification to the sponsor can be made by email and the email address is [contact]

CLINICAL INVESTIGATION PLAN

The investigator must ensure that all additional relevant information (i.e., radiology reports, hospitalization reports indicating the SAE) that becomes available is also forwarded to the sponsor immediately after the initial notification and the information should be de-identified.

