10.7.1. Peristomal skin lesions

Peristomal skin lesions are common and the incidences range from 20% to 50%.

Dermatoses included irritant reactions, particularly from leakage of urine or feces and pre-existing skin diseases, infections, allergic contact dermatitis, and pyoderma gangrenosum are less common. The classification of Borglund will be used to assess severity of the skin lesions the site. Photographs of the stoma and skin lesions will be taken as part of study documentation and for review by an independent panel if required.

Classification of peristomal skin complications (Borglund et al)

Category	Criterion	Additional explanation
E0/P0	No signs of irritative skin lesions; no obvious signs of erythema, erosion, or papular lesions	
E+/P0	Mild erythematous-erotic skin lesions E+/P0	This subgroup (E+) includes patients with dispersed papules lesions, and/or tiny, erythematous, macular lesions, vesicles, or tiny erosion.
E++/P0	Severe erythematous-erotic skin lesions.	The E++ subgroup includes patients with numerous papules and/or tiny macules, confluent erythematous macules, widely spread erosions, excoriations, and ulcerations.
E0/P+	Mild pseudoverrucous skin lesions	The mild (P+) pseudoverrucous skin lesion is characterized by dispersed, single, eruptive, or partly confluent, wart-like papules, or nodules located on the peristomal skin close to the mucocutaneous lining.
E0/P++	Severe pseudoverrucous skin lesions	The P++ reflects severe pseudoverrucous skin lesions and is a confluent, elevated ostomy circumference close to the ostomy mucosa.

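### Peristomal skin is neither graded nor photographed before implantation, so in subjects who already have a stoma the skin-lesion endpoint cannot separate old lesions from new by grade

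*Combined protocol and SAP*

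**What the plan says.** **Endpoint.** Sections 4.3 and 10.7 list, as a secondary safety endpoint, "Proportion of implanted subjects with peristomal skin lesions will be evaluated using a validated 5-point scale". The neighbouring adverse-event endpoint is limited to events that begin at or after implantation. The skin endpoint has no such limit and no comparison with baseline.

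**Scale.** Section 10.7.1 gives the tool, with no time point: "The classification of Borglund will be used to assess severity of the skin lesions the site". It has five categories, from no lesion to severe erythematous or severe pseudoverrucous change.

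**Collection.** Section 4.3 starts the clock in hospital: "Safety information will be collected during the following intervals: during hospitalisation, interval from discharge to 4-weeks visit". In the flow chart, the safety-evaluation and photograph rows are blank at screening and baseline and first marked on the procedure day. The photograph row is for views "of implant, stoma and adjacent skin". Sections 6.7 and 10.10.1 ask for photographs at discharge, and the list in 4.3 begins at 4 weeks.

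**Baseline visit.** Section 6.5 lists no skin grade and no photograph. It does put into the CRF any abnormal findings from the physical examination and from the stoma nurse: "Record if assessment by the stoma/research nurse has been performed and any abnormal findings".

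**Population.** Inclusion criterion 1 (5.1) admits people who already have a conventional end-ileostomy, a continent ileostomy or a pelvic pouch and need an alternative. Section 10.1 mentions people who cannot tolerate bags because of complications. Skin lesions are not an exclusion (5.2).

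**The concern.** The study has one arm, so a subject's own state before surgery is the only internal reference for skin. The plan uses such a reference for quality of life, which is measured at baseline, but not for skin.

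The gap falls on the subjects most likely to arrive with damaged skin, namely those whose present stoma is troublesome. Their lesions need not clear after surgery, because bags remain in use until at least the 8-week review (flow chart, note e). If such a lesion is seen at the Port site in the first postoperative interval, the data do not show whether it is the same, better or worse than before. At stake is whether a named safety proportion can be read as telling us about the device.

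**Working it through.** The plan states no figure on this point, so there is nothing to reproduce. The check is first one of text and then one of scale.

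**Step 1: is there any graded or photographic record of the skin before implantation?**

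| Possible source | What it provides | Does it serve as a baseline? |
|---|---|---|
| Flow chart, safety evaluation | First mark on the procedure day | No |
| Flow chart, photographs | First mark on the procedure day; the views include the implant | Not specified as pre-operative |
| 6.6.1 and 6.6.2 (preparation, procedure) | No instruction to photograph or grade the skin | No |
| 6.7 and 10.10.1 | Photographs at discharge | Early, but after implantation |
| 4.3 | Photographs from 4 weeks | No |
| 6.5 | Abnormal findings from examination and stoma nurse | Presence may be noted; no grade |

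No source gives a Borglund grade or a specified pre-operative image.

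**Step 2: does an analysis rule exclude old lesions?** The onset limit in 4.3 belongs to treatment-emergent adverse events. Section 8.4 says of an event present before consent that "only its worsening should be reported", but this governs adverse-event reporting. Neither rule is attached to the skin endpoint. Section 10.9 leaves derived variables to a statistical analysis plan still to be written. That plan could define new or worsened lesions, but it could not recover a grade that was never taken.

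**Step 3: who is affected?** Only subjects who have a stoma before surgery, have a lesion there, receive the Port at that site, and still have the lesion afterwards. A subject having a first ileostomy has no earlier peristomal skin. A pelvic-pouch subject need not have a stoma.

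**Step 4: scale (illustration only).**

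Fraction of all subjects with a carried-over lesion = share with an existing ileostomy × lesion prevalence before implantation × persistence at the Port site.

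- Number of subjects: 200 (section 5), all taken as implanted.
- Share: 25% to 50%. Assumption; not in the protocol.
- Prevalence: 20% to 50%. Section 10.7.1 gives this range as incidence; using it as prevalence is an assumption.
- Persistence: 50% to 100%. Assumption; not in the protocol.

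Low end: 0.25 × 0.20 × 0.50 = 0.025, which is 5 of 200 subjects.

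High end: 0.50 × 0.50 × 1.00 = 0.25, which is 50 of 200 subjects.

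The reported proportion rises by somewhat less, since some of these subjects would have developed a new lesion anyway. If q is the true new-lesion rate, the rise is the carried-over fraction × (1 − q). With q = 20% (assumed), the rise is 0.025 × 0.80 = 2 points at the low end and 0.25 × 0.80 = 20 points at the high end.

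A case inside the range: share 50%, prevalence 30% (the minimum frequency of skin irritation in section 1.1), full persistence, q = 20%. Reported proportion = 0.50 × (0.30 + 0.70 × 0.20) + 0.50 × 0.20 = 0.22 + 0.10 = 0.32. A true new-lesion rate of 20% would be reported as 32%.

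**The case against.** The strongest reply is that the plan is less bare than it looks.

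- **Baseline findings are recorded.** Diseased skin round a stoma is an abnormal finding, so section 6.5 should capture its presence, and the later analysis plan could use that. This stands for presence or absence. It does not supply a grade, and no rule yet uses the finding.
- **There are early photographs.** The day-0 and discharge images come before any use of the Lid, so a reader who inferred that a reviewing dermatologist has no reference image at all would go too far. The images help to judge later change. They do not show the skin before the Port.
- **Onset and cause have their own endpoints.** Treatment-emergent and device-related adverse events are reported separately, and investigators assess causality. This stands and limits the harm.
- **The endpoint is descriptive.** It has no success criterion and no test, and carry-over raises the any-lesion proportion, which works against the device. This also stands. An inflated safety proportion is still hard to interpret.
- **Conversions may be few, and stomas may be re-sited.** Section 3.1 emphasises patients having a first ileostomy, and 6.5 provides for siting. This is why the size cannot be fixed.

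A reader might also infer that the rule in 8.4 cannot be operated without a Borglund grade. The text does not support that: adverse-event severity is graded mild, moderate or severe (8.2), and 8.4 does not refer to Borglund. Nor is it a defect against the stated objectives that skin improvement cannot be shown. Section 7.2.1 lists freedom from appliance-related irritation only as a potential benefit, and improvement is not an endpoint.

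**Conclusion.** The point holds in a limited form. For subjects with an existing stoma, lesions that predate the Port and persist at its site can be counted in the skin endpoint and cannot be separated from new ones by grade. Subjects having a first stoma, and the primary endpoint, are untouched.

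It is tempting to go further and say that old lesions are counted as outcomes. The text permits that but does not state it: the endpoint has no onset rule in either direction, and the analysis plan is still to come.

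The size is unknown. The 2.5% to 25% of subjects shown above is an illustration. It depends on an undocumented conversion share, on incidence read as prevalence, and on assumed persistence at a reused site. The top of the range needs every assumption at its extreme. The gap in the schedule does not depend on these figures. It merits correction because the remedy is cheap and the missing grade cannot be obtained afterwards.

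**What to change.** 1. **Flow chart and 6.5.** For subjects with an existing stoma, record a Borglund grade and take the peristomal photographs at the baseline visit, after consent, alongside the physical examination and stoma-nurse assessment already held.
2. **4.3 and 10.7.** Report the proportion with new or worsened lesions versus baseline beside the any-lesion proportion.
3. **Analysis plan.** Define worsening. The Borglund categories run along two axes (erythematous and pseudoverrucous), so a step up on either axis would be a workable rule. State how a lesion is classed when the Port is placed at a different site from the old stoma.

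The cost is one eCRF field and one photograph set, for this subgroup only, at a visit that already takes place. If the operative form does not record whether the old site was reused, one further tick box is needed. Subjects enrolled before the change will lack the baseline grade and should be shown as missing in the new-or-worsened summary. The existing endpoint is kept as it is.

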4.4. Quality of Life Evaluation

Impact on quality of life will be evaluated by using two validated instruments EQ-5D-5L Quality of Life (QoL) questionnaire and Montreux Quality of Life questionnaire.

CLINICAL INVESTIGATION PLAN

Secondary endpoints are:

Change in quality of life from baseline at 8, 16, 24, 36 and 52 weeks post implantation will be assessed among subjects with the device *in situ*.

5. SUBJECT SELECTION

A minimum of 200 patients will be enrolled. These patients have an indication for a permanent ileostomy, e.g., ulcerative colitis, familial adenomatous polyposis coli, or other diseases requiring elective colectomy; or patients with a medical need for an alternative to an existing conventional ileostomy or continent ileostomy or pelvic pouch.

5.1. Inclusion Criteria (IC)

Subjects will be included if the following criteria are met:

- 1) Subject has ulcerative colitis, familial adenomatous polyposis coli or other diseases for whom a permanent ileostomy is indicated; or the subject has a medical need for an alternative to an existing conventional end-ileostomy, continent ileostomy or pelvic pouch; and
- 2) Patient is a male ≥ 18 years of age or female ≥ 18 years of age (note exclusion criterion 4 regarding female with childbearing potential); and
- 3) Signed written informed consent has been obtained prior to any study- related procedure.

5.2. Exclusion Criteria (EC)

Subject will be excluded if any one of the following conditions exists:

- 1) Concurrent gastrointestinal fistula, parastomal or incisional hernia, or a history of recurrent gastrointestinal fistula, recurrent parastomal hernia(s), and/or recurrent incisional hernia(s).
- 2) Patients with undetermined colitis.
- 3) Patients with Crohn's disease
- 4) Females who are of childbearing potential and do not wish to use birth control measures for the duration of the study
- 5) Patients receiving immunosuppressives, oncologic treatment or anticoagulants.
- 6) Any clinically significant, abnormal, baseline laboratory result which in the opinion of the surgeon, affects the patient's suitability for the study or puts the patient at risk if he/she undergoes surgery
- 7) Severe illness which, in the opinion of the surgeon may put the patient at risk when participating in the study or may affect the patient's ability to complete the study visits
- 8) Condition associated with the risk of poor protocol compliance, e.g. alcoholism and/or drug abuse, dementia, self-destructive personality disorder
- 9) Subjects who are underweight or obese with $BMI \leq 17 \text{ kg/m}^2$ or $BMI \geq 33 \text{ kg/m}^2$
- 10) Participate in other clinical studies that could interfere with the result in the ongoing study

CLINICAL INVESTIGATION PLAN

5.3. Subject Accountability

5.3.1. Enrolled subjects

The point of enrolment is the time at which, following recruitment, a subject signs and dates the informed consent to agree to participate in the clinical investigation. Subject for whom consent was not obtained prior to participation in the study will not be considered enrolled. No data from subject who has not provided signed informed consent will be included in any analysis.

5.3.2. Screen failures

A screen failure is a subject who does not meet all eligibility criteria and therefore will not be enrolled into the study and no informed consent form will be signed. A screening log will contain information on all subjects screened identified by the Subject Identification number. For screened failures, the eligibility criterion/ criteria that are not met will be recorded.

5.3.3. Treated Subjects

An enrolled subject who meets all eligibility criteria, and has been implanted with the TIES® Port will be followed in accordance with the protocol requirements.

Any enrolled subject in whom the TIES® Port implantation procedure is attempted but not successfully implanted will be followed for 6 months after the implantation procedure and then exit the study.

5.3.4. Withdrawal

Early termination of study participation will be documented for patients that have signed an informed consent form and who exited for any of the following reasons:

- Subject for whom the implantation procedure has been attempted but cannot completed, for example, due to technical reasons. (These subjects will be followed for six months.)
- Subject who are explanted. (These subjects will be followed for six months.)
- Subject no longer wishes to continue with the study follow-up. No further follow up applies.
- Investigator believes it is the best medical interest of the subject to discontinue study participation due to safety reasons. (These subjects will be followed until study procedure related adverse events have resolved.)
- Death of the subject.

No additional subjects will be recruited to compensate for subjects who withdraw or are withdrawn from the study.

6. STUDY PROCEDURES AND ASSESSMENTS

6.1. Subject Identification

Each subject will be given a Subject Identification Number for tracking purposes from screening, enrolment and throughout study participation. Use of a Subject Identification

CLINICAL INVESTIGATION PLAN

Number is intended to assure confidentiality for subjects. Subject numbers will be issued chronologically by the EDC following signed informed consent.

